2. OBJECTIVES AND DESIGN

2.1 Trial Objectives

2.1.1 Primary Objective

The primary objective of this trial is to demonstrate the contraceptive efficacy of LF111.

2.1.2 Secondary Objectives

The secondary objectives of this trial are to demonstrate the safety and tolerability of LF111 and to assess the pharmacokinetics of LF111.

2.2 Trial Endpoints

2.2.1 Primary Efficacy Endpoints

The primary efficacy endpoint will be the Pearl Index (PI) based on evaluable cycles in non-breastfeeding women aged ≤ 35 years (at the time of trial enrolment).

PI = number of pregnancies*1300/number of evaluable medication cycles

An evaluable cycle is a cycle with intercourse without back-up contraceptive at least once per month based on the electronic diary question 'Did you have sexual intercourse since the beginning of the cycle?' and will be included in the primary analysis. If the cycle is not evaluable but the subject became pregnant in this cycle, the cycle has to be included in the analysis.

Pregnancies following premature termination of IMP will be excluded from the calculations if the estimated date of conception occurs later than seven days after the last tablet intake (active or placebo).

Date of conception will be determined by using the following information:

1. Ultrasound (the date of conception must be based on the most accurate method i.e. the first trimester ultrasound. Subsequent ultrasounds will not be allowed to change dating based on this initial assessment).
2. Ultrasound (in case the first trimester ultrasound was not performed)
3. Quantitative β -hCG
4. Qualitative urine β -hCG determination
5. Estimation of gestational age based on pelvic and/or abdominal examination or pregnancy outcome
6. Investigator's estimation in the absence of the above criteria

Medication cycle will be defined as 28 days starting with the administration of the first tablet from the blister containing 28 tablets and ending with the last day of intake.

2.2.2 Secondary Efficacy Endpoints

Cycles of breastfeeding women will be excluded from the efficacy analyses but included in the analyses regarding safety and tolerability.

Secondary efficacy endpoints are:

- Pearl Index based on overall cycles (overall PI) in women aged ≤ 35 years
PI based on overall cycles will include all pregnancies which will occur during the trial in women aged ≤ 35 years (at the time of trial enrollment).
- PI for method failures in women aged ≤ 35 years
Method failures PI will include all pregnancies of women who used the IMP correctly. Pregnancies are to be excluded from the calculation if in medication cycles of conception or in the previous medication cycles depending on the date of conception:
 - not all active tablets are taken (based on returned medication, recordings in the e-diary and non-compliance based on DRSP levels, if necessary)

- there is a tablet free interval between the previous medication cycle and the medication cycle of conception
- vomiting or diarrhea is documented
- administration of prohibited prior or concomitant therapy as detailed in Section 10.7 of the Clinical Trial Protocol is documented
- Pregnancy ratio in women aged ≤ 35 years (Life table analysis)

In addition to PI analysis, method failure life table analysis and life table analysis on evaluable cycles will be performed in women aged ≤ 35 years (at the time of trial enrollment) in order to have the pregnancy rate at each cycle and cumulative pregnancy rates for 6 and 13 cycles. For life table analysis on evaluable cycles, only medication cycles of non-breastfeeding women will be considered as evaluable as defined in 2.2.1 and will be included in analysis. If the cycle is not evaluable but the subject became pregnant in this cycle, the cycle has to be included in the analysis. All pregnancies following premature termination of IMP will not be included in calculations if they occur later than seven days after the last tablet intake (active or placebo). Method failure pregnancy rates similar to method failure PI will include only those cycles of women who use the IMP correctly and include only perfect medication cycles as described in Section 5.5 of non-breastfeeding women.

- Overall PI, PI for method failures, PI for evaluable cycles and pregnancy ratio (life table analysis) in all women

All analyses described above in women aged ≤ 35 years (at the time of trial enrollment) will also be evaluated for the whole subject population. Included are only cycles of non-breastfeeding women with sexual activity without using back-up contraception.

- Overall PI, PI for method failures, PI for evaluable cycles and pregnancy ratio (life table analysis) in women aged > 35 years

All analyses described above in women aged ≤ 35 years (at the time of trial enrollment) will also be evaluated for women aged > 35 years at study enrollment. Included are only evaluable cycles of non-breastfeeding women with sexual activity without using back-up contraception.

Overall PI will be based on exposure cycles.

Efficacy Endpoints in Addition to the Protocol

- Overall PI based on only confirmed and on confirmed and suspected, non-confirmed pregnancies (with and without sites 104 and 120)

Overall PI based on exposure cycles will be evaluated for the whole subject population. Included are only cycles of non-breastfeeding women. The overall PI will be evaluated based on only confirmed pregnancies and on confirmed and suspected, non-confirmed pregnancies and in- and excluding sites 104 and 120.

All analyses described above will be evaluated in addition by BMI subgroup and by weight subgroup.

- PI for evaluable cycles in women aged ≤ 35 years in total and by BMI and weight groups (with and without sites 104 and 120) based on confirmed and on confirmed and suspected, non-confirmed pregnancies

PI based on evaluable cycles will be evaluated in women aged ≤ 35 years. Included are only cycles of non-breastfeeding women. The PI will be evaluated based on only confirmed pregnancies and on confirmed and suspected, non-confirmed pregnancies and in- and excluding sites 104 and 120.

All analyses described above will be evaluated in addition by BMI subgroup and by weight subgroup.

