Method failure pregnancy*	All on-drug pregnancies of women who used the IMP correctly. Pregnancies are to be excluded from the calculation if in medication cycles of conception or in the previous medication cycles depending on the date of conception: 
 - not all active tablets are taken (based on returned medication, recordings in the e-diary and non-compliance based on DRSP levels, if necessary) - there is an active tablet free interval between the previous medication cycle and the medication cycle of conception. Tablet free interval will be determined by record from treatment diary. - vomiting or diarrhea is documented - administration of prohibited prior or concomitant therapy as detailed in Section 10.7 of the Clinical Trial Protocol is documented
Exposure cycles	28-day cycles, where at least one treatment diary entry of IMP intake is available. In addition, a cycle will be an exposure cycle if the subject become pregnant during this cycle regardless this cycle was a 28-day cycle or not.
Evaluable cycle	Cycles are exposure cycles with intercourse without back-up contraceptive at least once per cycle based on electronic diary question 'Did you have sexual

	
intercourse since the beginning of the cycle?" and answered with: 'Yes I had sexual intercourse without additional contraception'.
 
Also, cycle is to be defined as evaluable if:
 
 - Subject became pregnant at the respective cycle regardless back-up contraception was used or not. - Cycle has missing answer about intercourse or answered "I had NO sexual intercourse at all" but subject became pregnant at the respective cycle. 
Cycle will not be defined as evaluable if subject did not become pregnant and:
 
 - The question was answered with 'Yes I had sexual intercourse with additional contraception'. - Cycles with NO intercourse. - Cycle has missing answer about intercourse.
Perfect cycle*	
Evaluable cycles which have no:
 
 - >48h tablet free interval during the second IMP intake till day 24 of each cycle or >144h interval between the last IMP intake and the first IMP intake in consecutive cycles. Tablet free interval calculation will not take into account cycle days 25-28. - 4 or more days with forgotten tablets intake during 1-24 cycle days. - Protocol deviations having effect on this cycle.

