* Method failure pregnancies will be only those which occurred during the perfect cycles, e.g., if pregnancy will contradict method failure definition then the cycle in which pregnancy occurred could not be called perfect cycle and vice versa.

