5.5.2 Secondary Efficacy Analysis

Secondary Efficacy Analysis will be based on non-breastfeeding women. Also, analysis will be performed in BMI subgroups.

Overall PI

Overall PI will be calculated based on exposure cycles for all women, aged ≤ 35 years and aged > 35 years:

$$PI \text{ (exposure cycles)} = \frac{\sum \text{on-drug pregnancy} \in \{\text{exposure cycles}\}}{\#\{\text{exposure cycles}\}} \times 1300.$$

Respective two-sided 95% CI for overall PI will be calculated according to formula in Section 5.5.

PI for method failures

PI for method failures will be calculated based on perfect cycles for all women, aged ≤ 35 years and aged > 35 years. Number of pregnancies will be calculated according to method failure definition:

$$PI (method failure) = \frac{\sum \text{method failure pregnancy} \in \{\text{perfect cycles}\}}{\#\{\text{perfect cycles}\}} \times 1300.$$

Respective two-sided 95% CI for PI for method failures will be calculated according to formula in Section 5.5.

Evaluable cycles PI

Evaluable cycles PI will be calculated based on evaluable cycles for all women and women aged > 35 years:

$$PI (\text{evaluable cycles}) = \frac{\sum \text{on-drug pregnancy} \in \{\text{evaluable cycles}\}}{\#\{\text{evaluable cycles}\}} \times 1300.$$

Respective two-sided 95% CI for PI based on evaluable cycles will be calculated according to formula in Section 5.5.

Life table analysis for pregnancy rate

Method failure life table analysis and life table analysis on evaluable cycles will be performed in all women, women aged ≤ 35 and > 35 years in order to have the pregnancy rate at each cycle and cumulative pregnancy rates for 6 and 13 cycles.

Cumulative pregnancy rate will be calculated by using the **PROC LIFETEST** procedure:

```
PROC LIFETEST DATA=<data set> METHOD=KM OUTSURV=CL CONFTYPE=LOG;
      TIME <time variable>*<censorship flag>(1);
      RUN;
```

The Kaplan-Meier method will be used to estimate the cumulative pregnancy ratio. Logarithmic transformation will be used for 95% CI of the pregnancy rate. The period from the start of treatment until the pregnancy will be the time variable in this analysis. Subjects who did not become pregnant will be censored at their time of the last intake of IMP.

Tables

No.	Name	Analysis set	Comments

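### Method-failure Pearl Index: apart from a >144h boundary gap and data-review discretion, previous-cycle events can disqualify a pregnancy but not a pregnancy-free cycle with the same history

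*SAP*

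**What the plan says.** The protocol synopsis lists the PI for method failures as a secondary efficacy criterion. The SAP builds it from two definitions.

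**Numerator.** SAP 2.2.2 and the definitions table in 5.5 exclude a pregnancy when certain events are found "if in medication cycles of conception or in the previous medication cycles depending on the date of conception". The events are incomplete intake, worded as "not all active tablets are taken (based on returned medication, recordings in the e-diary and non-compliance based on DRSP levels, if necessary", a tablet-free interval between the previous cycle and the cycle of conception, documented vomiting or diarrhea, and prohibited therapy. No conception date is given at which the search moves back a cycle, and no limit is set on how many previous cycles are searched.

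**Denominator.** SAP 5.5.2 states: "PI for method failures will be calculated based on perfect cycles for all women, aged ≤ 35 years and aged > 35 years". Under 5.5 a perfect cycle is an evaluable cycle with none of the following:
- ">48h tablet free interval during the second IMP intake till day 24 of each cycle"
- ">144h interval between the last IMP intake and the first IMP intake in consecutive cycles"
- "4 or more days with forgotten tablets intake during 1-24 cycle days"
- "Protocol deviations having effect on this cycle"

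**Footnote.** SAP 5.5 links the two: "Method failure pregnancies will be only those which occurred during the perfect cycles". It adds that a pregnancy failing the method-failure definition takes perfect status away from the cycle in which it occurred. It says nothing about cycles without a pregnancy.

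**The concern.** A method-failure PI is meant to estimate the pregnancy rate under correct use. That requires correct use to be defined identically whether or not the woman conceived. Here the time window searched for incorrect use can be longer for a pregnancy than for a pregnancy-free cycle. Pregnancies that follow a flawed cycle can leave the numerator while pregnancy-free cycles that follow a flawed cycle stay in the denominator.

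The issue is the length of the window. It is separate from the difference in missed-tablet limits (any missed active tablet for a pregnancy, but four or more forgotten days or a gap above 48h for a cycle). Using one limit on both sides would leave the window mismatch in place.

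At stake are the three method-failure PI tables (15.2.1.3.1 to 15.2.1.3.3), and possibly the method-failure life tables, which also draw on perfect cycles.

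**Working it through.** **The plan's own figure.** The plan gives no expected method-failure PI and no expected number of perfect cycles. Its only planning figure is 920 subjects for 5000 evaluable cycles (SAP 2.6). If dropouts contribute no cycles, 5000 / (13 x 0.752 x 0.55) = 930, about 1% from 920. That reproduces the stated size but does not bear on this point.

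**Step 1: one history, two outcomes.** Suppose five active tablets are missed mid-blister in cycle 6, and cycle 7 is flawless and evaluable.

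| | No pregnancy in cycle 7 | Conception early in cycle 7 |
|---|---|---|
| Own gaps and forgotten days | clean | clean |
| >144h gap at the boundary | none | none |
| Cycle 6 searched by a written rule | no | may be, depending on conception date |
| Cycle 7 perfect | yes, unless the data review intervenes | no, if cycle 6 is searched (footnote) |

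**Step 2: effect on the PI.** Let N be the number of evaluable cycles that pass the perfect-cycle rules on their own record, and h the conception risk in a cycle that follows a clean one. Let q be the share of the N cycles that follow a flawed cycle, r the relative conception risk in those cycles, and a the share of pregnancies in those cycles that are looked back and excluded.

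- SAP rule: pregnancies counted = N h [(1 - q) + q r (1 - a)]. The denominator is essentially N, since the footnote removes only one cycle per disqualified pregnancy. PI = 1300 h [(1 - q) + q r (1 - a)].
- Both sides judged on the cycle itself: PI = 1300 h [(1 - q) + q r].
- Both sides judged with the look-back: N h (1 - q) pregnancies over N (1 - q) cycles, so PI = 1300 h.

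SAP against the cycle itself: ratio = 1 - q r a / (1 - q + q r). This is never above 1.

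SAP against the symmetric look-back: ratio = 1 - q + q r (1 - a). This is below 1 exactly when r (1 - a) < 1. With assumed values:

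| q | a | r | Ratio |
|---|---|---|---|
| 0.10 | 0.5 | 1 | 1 - 0.10 + 0.05 = 0.95 |
| 0.30 | 0.5 | 1 | 1 - 0.30 + 0.15 = 0.85 |
| 0.30 | 0.5 | 2 | 1 - 0.30 + 0.30 = 1.00 |
| 0.30 | 0.5 | 3 | 1 - 0.30 + 0.45 = 1.15 |

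**Step 3: does the >144h criterion close the gap?** It is the one written criterion that crosses the cycle boundary. A simulation of 13 cycles with 24 active days used women of differing adherence and assumed mean daily miss rates of 1%, 2% and 4%. Of the cycles following a cycle with a missed active tablet, the boundary criterion made only 0.3%, 0.8% and 1.9% non-perfect. It barely reduces the asymmetry.

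**Step 4: how uncertain is q?** In the same simulation, 17%, 28% and 41% of cycles passing the tablet rules followed a cycle with at least one missed active tablet. Those figures treat any miss as a flaw. If the previous cycle is instead held to the perfect-cycle limits and tablets are taken at a fixed time, a single missed tablet leaves a gap of exactly 48h and does not count. Then q is about 5% or less. If half of single misses stretch past 48h, q starts at about 9% at the lowest miss rate. The result depends heavily on a choice that the documents do not settle.

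**The case against.** **The cycle is not judged on its own days alone.** A reader might infer that it is. The documents do not support that: the >144h criterion spans two cycles, and the deviation criterion sets no limit in time. SAP 3.3 has a team including a physician decide which deviations affect a perfect cycle, and its listings cover vomiting or diarrhea, prohibited therapy and gaps above 48h. This stands as a qualification. It does not cure the asymmetry, because nothing tells the meeting to look back for pregnancy-free cycles. The meeting also assigns pregnancies to category and cycle after database lock in an open-label trial, so the outcome is known.

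**The look-back is conditional.** The cycle 7 pregnancy in the example may be excluded; the text does not say that it must be. If the meeting assigned an early conception to cycle 6, that cycle would be non-perfect on its own record for either outcome, and the asymmetry would shrink. This stands, and it is a reason to write the rule down.

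**The bias need not always be downward.** A reader might infer that it must be. That holds against judging both sides on the cycle itself. Against a symmetric look-back it fails once r (1 - a) reaches 1, for example r = 2 with a = 0.5.

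**A 40% understatement is not supported.** It needs q = 0.40, which resembles an any-miss rate, and a = 1, which would leave the conception-date condition without effect.

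**The endpoint is secondary and exclusions are reported.** Tables 15.1.7.1.1 and 15.1.7.1.2 will show excluded pregnancies and cycles. They will not show the pregnancy-free cycles that a matching look-back would have excluded.

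**Conclusion.** The point holds in a limited form. Previous-cycle events can exclude a pregnancy from the method-failure PI. Beyond the >144h gap and whatever the data review chooses to carry forward, no rule excludes a pregnancy-free cycle with the same history, and the footnote makes perfect status depend on outcome.

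Compared with judging both sides on the cycle itself, the effect can only be to lower the PI. Compared with a symmetric look-back, it lowers the PI whenever r (1 - a) < 1. The documents give none of q, a and r, so the size is unquantified. The 5% and 15% figures illustrate a = 0.5 with equal conception risk (r = 1) and are not estimates.

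A reader might also infer that the method-failure life table is biased in the same way. That is not shown. SAP 2.2.2 restricts it to perfect cycles, but 5.5.2 describes a subject-level Kaplan-Meier analysis censored at last intake and does not say how perfect cycles enter it.

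This should be corrected because it affects what a listed secondary endpoint means. The primary PI, based on evaluable cycles, is untouched.

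**What to change.** In SAP 2.2.2 and 5.5, replace the conception-date condition with one explicit look-back window and apply it identically to every cycle, blind to pregnancy. The simplest version for the analysis is:

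- A cycle is perfect only if it and the preceding cycle are free of the disqualifying events. Cycle 1 is judged on its own days.
- A method-failure pregnancy is one conceived in a cycle that is perfect by that rule.
- The same flag is used wherever perfect cycles enter the method-failure life table.

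A full preceding cycle for every conception would exclude some late-cycle conceptions after a distant miss. A shorter window also removes the asymmetry, provided that it is written down and is the same on both sides. Any deviation that the data review carries forward should likewise be decided without knowledge of pregnancy.

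The cost is SAP wording, one lagged flag in the cycle dataset, fewer perfect cycles and a somewhat wider confidence interval.

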2.2.3 Safety Endpoints

Analysis of safety endpoints will be conducted using the SS only.

- AEs

All AEs will be summarized by number and proportion of subjects and number of AEs. TEAEs will be summarized by calculating the number and percent of subjects with AEs by MedDRA primary system organ class (SOC) and preferred term (PT). Also, TEAEs will be summarized by severity and relationship to treatment. Number and percent of subjects with serious TEAEs, TEAEs leading to trial termination and TEAEs of special interest will be provided by MedDRA PT and SOC.

- Vital signs

Summary statistics for absolute values and absolute change from V1a (baseline) will be provided for each visit (V1b to V6/EDV).

- Clinical laboratory parameters

Laboratory parameters will be summarized by calculating summary statistics on the absolute values and on the change from V1a to V3, V4, V5 and V6. Shift tables will be provided to illustrate changes with respect to the laboratory normal ranges between V1a and V6/Early discontinuation visit (EDV). The number and percent of subjects with values outside the limits of clinical significance reference ranges will be summarized.

2.2.4 Tolerability endpoints

The tolerability endpoints are based on vaginal bleeding pattern and include the following variables:

Bleeding:

- Number of subjects with bleeding by treatment day, treatment cycle and reference period (summary of cycles 2-4, 5-7, 8-10, 11-13 and 2-13)
- Number of subjects with unscheduled bleeding days by treatment cycle and reference period
- Number of subjects with scheduled bleeding days by treatment cycle and reference period
- Number of subjects with prolonged bleeding >nine days/ >14 days by reference period
- Number of bleeding episodes during treatment and by reference period
- Number of days with bleeding by cycle and reference period
- Number of days with unscheduled bleeding by cycle and reference period
- Number of days with scheduled bleeding by cycle and reference period
- Mean length of bleeding episodes by cycle and reference period

Spotting:

- Number of subjects with spotting by treatment day, treatment cycle and reference period (summary of cycles 2-4, 5-7, 8-10, 11-13 and 2-13)
- Number of subjects with unscheduled spotting days by treatment cycle and reference period
- Number of subjects with scheduled spotting days by treatment cycle and reference period
- Number of subjects with prolonged spotting >nine days/ >14 days by reference period
- Number of spotting episodes during treatment and by reference period
- Number of days with spotting by cycle and reference period
- Number of days with unscheduled spotting by cycle and reference period
- Number of days with scheduled spotting by cycle and reference period
- Mean length of spotting episodes by cycle and reference period

Only cycles of women with complete and correct diary entries will be taken into account in the analysis.

All tolerability variables will be evaluated over 13 cycles.

Another tolerability endpoint is the IMP acceptability.

Tolerability Endpoints in Addition to the Protocol

In addition, tolerability endpoints that are based on vaginal bleeding pattern and on combined variables (bleeding/spotting) will be evaluated:

- Number of subjects with bleeding/spotting by treatment day, treatment cycle and reference period
- Number of subjects with unscheduled bleeding/spotting days by treatment cycle and reference period
- Number of subjects with scheduled bleeding/spotting days by treatment cycle and reference period
- Number of subjects with no bleeding/spotting days by treatment cycle and reference period
- Number of days with bleeding/spotting by cycle and reference period by BMI subgroup
- Number of days with unscheduled bleeding/spotting by cycle and reference period by BMI subgroup
- Number of days with scheduled bleeding/spotting by cycle and reference period by BMI subgroup
- Number of days with bleeding/spotting by cycle and reference period by weight subgroup
- Number of days with unscheduled bleeding/spotting by cycle and reference period by weight subgroup
- Number of days with scheduled bleeding/spotting by cycle and reference period by weight subgroup

